7.3 Reporting procedures for Serious Adverse Events

0968 STIM-HD WP1 Protocol Version 1.2 29 Jan 2025 IRAS: 347115

It is expected that participants will experience a significant number of underlying health conditions and consequently an increased number of expected hospital admissions. In addition, expected events may occur related to the NMES intervention. NMES induces a muscle contraction via the delivery of a small electrical current. This may cause the muscles to feel sore the next day. There have been several previous studies of NMES in chronic disease patients, including haemodialysis patients that have reported very low rates of SAEs. A recent systematic review and meta-analysis performed by NICE has concluded NMES is safe to use in chronic disease population.

Therefore, only SAEs that are clearly related to the study and of a serious nature will be subject to expedited reporting to the Sponsor. These SAEs include:

- Musculoskeletal injury as a direct result of the outcome assessments or the intervention (NMES)
- Anything else in the investigator's opinion that is related, serious, and unexpected.

These SAEs, occurring from the time of randomisation until end of assessment period, will be reported to the Sponsor immediately and within 24 hours of becoming aware of the event. The following information will be collected:

- full details in medical terms and case description
- event duration (start and end dates, if applicable)
- action taken
- outcome
- seriousness criteria
- relationship to the study procedure or intervention

All other SAEs will be recorded using the SAE Log, which will be kept in the Trial Master File.

Deaths will be recorded as part of the study outcomes and therefore will not be subject to expedited reporting.

SAEs will be reported using appropriate forms and according to the Sponsor SOP for reporting serious adverse events. Additional information will be provided if requested to the Sponsor and main Research Ethics Committee (REC). The Principal Investigator or another delegated physician (as agreed by the Sponsor) is responsible for the review and sign off of the SAE and the assessment of causality (i.e. whether an event is related to a study procedure or intervention).

The Sponsor will perform an initial check of the information and ensure that the SAE line listing is reviewed by the Director of Research & Innovation. All SAE information must be recorded on an SAE form and sent to the Sponsor. Additional information received for a case (follow-up or corrections to the original case) needs to be detailed on a new SAE form and sent to the Sponsor.

Copies of all documentation and correspondence relating to SAEs will be stored in the TMF and/or ISF.

Any change of condition or other follow-up information should be emailed to the Sponsor immediately and within 24 hours of the information becoming available. Events will be followed up until the event has resolved or a final outcome has been reached.

All SAEs will be tabulated and summarised, according to system organ class and preferred term, as classified in the Medical Dictionary for Regulatory Activities (MedDRA). No formal statistical testing will be performed. All events will be summarised by seriousness, expectedness and relatedness.

Some SAEs are expected as part of the study, these include: muscle soreness, fatigue, and discomfort. Whilst these SAEs will be recorded as per the described procedures, they will not be reported to the Sponsor.

The Sponsor will report all SUSARs to the Research Ethics Committee concerned. Fatal or life-threatening SUSARs must be reported within 7 days and all other SUSARs within 15 days. The CI will inform all investigators concerned of relevant information about SUSARs that could adversely affect the safety of participants.

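### WP1 section 7.3 calls soreness, fatigue and discomfort SAEs and exempts them from Sponsor reporting, so a related serious event recorded under one of those names gets opposite instructions

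*Protocol*

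**What the plan says.** All of this is in the WP1 protocol, section 7.3, unless stated otherwise.

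- **The exemption.** "Some SAEs are expected as part of the study, these include: muscle soreness, fatigue, and discomfort". The next sentence reads: "Whilst these SAEs will be recorded as per the described procedures, they will not be reported to the Sponsor".
- **The general rule.** "All SAE information must be recorded on an SAE form and sent to the Sponsor". Follow-up is treated the same way: "Any change of condition or other follow-up information should be emailed to the Sponsor immediately and within 24 hours of the information becoming available". Neither sentence carries an exception.
- **The expedited route.** SAEs that are clearly related to the study and serious go to the Sponsor quickly. Two categories are listed. The first is musculoskeletal injury resulting directly from the assessments or from NMES. The second is "Anything else in the investigator's opinion that is related, serious, and unexpected". These "will be reported to the Sponsor immediately and within 24 hours of becoming aware of the event".
- **The remaining SAEs.** "All other SAEs will be recorded using the SAE Log, which will be kept in the Trial Master File".
- **The definition (section 7.1).** An SAE is an event that is fatal or life-threatening, requires or prolongs inpatient care, causes lasting or significant disability, is a congenital anomaly, or is otherwise medically important.

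**The concern.** SAE is a defined term in this protocol, and section 7.1 adds a note separating serious from severe. An event that section 7.3 calls an SAE is therefore serious by definition. The exemption is attached to that term twice, in consecutive sentences, and it removes Sponsor reporting as such.

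The Sponsor's knowledge of such an event is what is at stake. WP1 was set up because the patient group was worried about discomfort from NMES (section 12.3), and a 228-participant trial of NMES is planned in the same programme. A related event of soreness or discomfort bad enough to be serious is one the Sponsor would want to hear of promptly. The WP1 text names a Trial Management Group and no independent safety committee, whereas the main trial has a DSMC that reviews SAE data. In WP1 the Sponsor is thus the principal check outside the investigator team.

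**Working it through.** No arithmetic applies. The check sets the rules side by side and follows one event through them: a WP1 participant has a serious event (for example, one needing admission) that the investigator judges clearly related to NMES.

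**Case A: the event is recorded as musculoskeletal injury.** The first expedited category applies. It carries no condition that the event be unexpected, so the Sponsor is told within 24 hours. There is no gap.

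**Case B: the event is recorded as muscle soreness, fatigue or discomfort.**

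| Rule in WP1 section 7.3 | Instruction for this event |
|---|---|
| Expedited category 1, musculoskeletal injury | Does not apply by name, because the event was not recorded as an injury |
| Expedited category 2, related, serious and unexpected | Uncertain: the event is related and serious, but the section has labelled it expected in advance |
| SAE Log for all other SAEs | Record on the log in the Trial Master File |
| All SAE information on a form to the Sponsor | Send |
| Follow-up information within 24 hours | Send |
| Exemption for the three named symptoms | Record, but do not report to the Sponsor |

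Two rules say send and one says do not send. The section gives no order of precedence.

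**Could the exemption mean only that expedited reporting is waived?** It does not say so. Where the section intends that limit it states it: deaths are excluded specifically from expedited reporting. The exemption has no such qualifier.

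**Is it standard text for this programme?** The parallel section of the main-trial protocol (10.3) also requires all SAE information to go to the Sponsor on a form, and it has no exemption for named symptoms. The exemption is specific to WP1.

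**Does the event disappear from the data?** No. The exempting sentence itself requires recording, and section 7.3 has all SAEs tabulated and summarised by seriousness, expectedness and relatedness.

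**A second tension in the same section.** The SAE Log sentence describes a tier of SAEs that are logged in the Trial Master File, with no mention of sending them on. The general rule says all SAE information is sent to the Sponsor. The two can be made compatible, but the section does not say how. Correcting the exemption alone would leave that open.

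**The case against.** The strongest answer is that this is a slip of terminology. Soreness and discomfort are routine effects of NMES, section 7.3 describes muscles feeling sore the next day, and both symptoms are study outcomes on a numerical rating scale. The writer almost certainly meant non-serious AEs. That is very likely right about intent and it shapes the fix, but site staff follow the text, and the text says SAEs twice.

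A reader might go further and infer that serious muscle harm from NMES would be withheld from the Sponsor. The documents do not support that, for four reasons, all of which stand.

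- An event recognised as musculoskeletal injury from NMES is expedited whether or not it was expected.
- Expectedness need not follow from the label alone. Section 7.1 ties it, for SUSARs, to nature and severity, and section 12.4 expects soreness to dissipate within a few days. Soreness needing admission could reasonably be judged unexpected in severity. The definition is written for medicinal products, so this is a reading by analogy, and the advance label pulls the other way.
- The Principal Investigator or a delegated physician reviews and signs off each SAE, so a medical judgement intervenes.
- The exempted events are recorded and summarised. The SAE Log sits in the Trial Master File, which the University of Leicester maintains (section 10), and that university is the Sponsor (section 10.1).

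These points reduce the consequence to one of notification. They do not remove the contradiction in Case B.

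**Conclusion.** The inconsistency is real and confined to the WP1 protocol. As written, section 7.3 exempts events that are serious by the protocol's own definition, against an unqualified rule in the same section. The practical gap is a study-related serious event recorded as soreness, fatigue or discomfort and not as musculoskeletal injury. For that event the instructions conflict, and the expedited category for unexpected events may not catch it. Prompt notification of the Sponsor is at risk; the record and its place in the summary tables are not.

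The size is small in numbers. WP1 plans 24 participants (section 8.1), and section 7.3 cites very low SAE rates in earlier NMES studies without giving a figure, so no expected count can be stated. Sample size, power, significance level and the outcome analyses are unaffected. The point is still worth correcting because it concerns safety reporting and the correction costs almost nothing.

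The conclusion assumes that SAE carries its section 7.1 meaning throughout, and that no Sponsor procedure outside this document already settles the conflict.

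**What to change.** In WP1 section 7.3:

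1. In both sentences of the exempting paragraph, replace 'SAEs' with 'non-serious AEs'.
2. Add a sentence: soreness, fatigue or discomfort that meets a seriousness criterion and is clearly related to the study procedures or NMES follows the section's existing expedited route to the Sponsor. Such an event that is serious but unrelated follows the section's ordinary SAE route. The relatedness condition matters: the section limits expedited reporting to clearly related events and expects many admissions from underlying illness, so a rule without it would create a new conflict.
3. Reconcile the SAE Log sentence with the rule that all SAE information goes to the Sponsor on a form, by stating which SAEs need a form sent, when, and which are only logged.

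The cost is a few lines in a wording amendment, with no change to visits, data items or analysis. If WP1 visits are already complete (the planned period ended on 25/07/2025), the Sponsor can instead check the SAE Log for any event not reported because of this sentence.

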7.4 Reporting Urgent Safety Measures

The Sponsor, the CI or the local PI at a research site may take appropriate urgent safety measures in order to protect research participants against any immediate hazard to their health or safety. If any urgent safety measures are taken, the CI/Sponsor shall be notified immediately, and in any event no later than 3 days from the date the measures are taken, give written notice to the Sponsor and the relevant REC of: the measures taken; reason these measures were taken; the circumstances giving rise to those measures and the plan for further actions.

8 Statistics and Analysis

8.1 Sample size calculation

A sample size of 24 participants will be utilised, as for pilot studies, a sample size of between 24-50 has been recommended (11,12). Purposeful sampling will be undertaken to ensure a representative sample. To ensure the study is appropriately powered, each component will be treated separately; that is, if a given participant does not complete all visits within a given component, a replacement will be recruited.

8.2 Statistical analysis plan

A statistical analysis plan (SAP) will be prepared by the Trial Statisticians and will contain full details of all statistical analyses. The SAP will be agreed with appropriate oversight prior to database lock. Any changes to the original SAP will be detailed along with the reason(s) for changes in subsequent SAPs.

8.2.1 Outcome analysis

To assess the optimal stimulation configuration for maximal evoked force with minimal discomfort a linear regression with evoked muscle force at NRS 4/10 will be compared among different combinations of stimulation parameters. To assess the change in muscle function and discomfort in response to different NMES protocols using the optimised stimulation configuration a linear regression with a change in an outcome variable (voluntary and evoked force, NRS) will be compared between the two NMES protocols and a control.

All data analyses will be performed in R (R studio, R foundation for Statistical Computing, Vienna, Austria) on an encrypted university computer.

8.3 Interim analysis and criteria for the premature termination of the study

0968 STIM-HD WP1 Protocol Version 1.2 29 Jan 2025 IRAS: 347115

No formal stopping rules or interim analyses have been pre-defined or planned. No criteria for early termination of the study have been set.

8.4 Participant population

We will recruit haemodialysis patients (either home or unit based) who have been receiving dialysis for more than 3 months.

8.5 Procedure(s) to account for missing or spurious data

For primary outcome, if <5% of data is missing, a complete case analysis will be performed. If more than 5% of data for the primary outcome is missing, multiple imputation will be performed.

9 Data Management

9.1 Data flow diagram

This is a separate PDF document.

9.2 Source data

Source documents are where data are first recorded, and from which participants' CRF data are obtained. These include, but are not limited to, consent forms, laboratory results and records. A master copy of the original data will be stored on which no analysis will be performed.

CRF entries will be considered source data if the CRF is the site of the original recording (e.g. there is no other written or electronic record of data). All documents will be stored safely in confidential conditions. On all study-specific documents, other than the signed consent, the participant will be referred to by the study participant number/code, not by name. All source data will be stored at Loughborough University, in safe conditions (locked filling cabinets in Pl's office).

9.3 Data collection tools, handling and record keeping

Each participant will be assigned a unique identification number upon consent and this will be added to all study documents/data collection tools in place of the participant's name.

Force data will be recorded in a digital form and stored on Loughborough University's cloud-based service (OneDrive). The remaining study data will be entered onto a paper Data Log before being entered into the study database stored on Loughborough University computer. Access to the database will be restricted to study staff using a username and password. A copy of the completed participant informed consent form and participant information sheet will be placed in the Trial Master File/Investigator Site File.

A contacts database (which contains participant contact details) will be held separately from the study database for the purposes of contact for future ethically approved research and providing a copy of the study results. Participant's contact details will be held securely at the Loughborough University in accordance with data protection regulations. This will be password protected and managed at site by the research team. Contact details will be deleted once they have been used for their agreed purpose; therefore they might be kept beyond the standard retention period of 6 years.

All data handling and record keeping will be kept in adherence to University of Leicester's, Loughborough University's, and relevant NHS Organisation(s) policies. All

study documentation containing identifiable patient data will be managed in accordance with ICH-GCP, The UK Policy for Health and Social Care Research and the Data Protection Act.

9.4 Access to data

Direct access will be granted to authorised representatives from the Sponsor, host institution and the regulatory authorities to permit study-related monitoring, audits and inspections in line with participant consent.

The Chief Investigator and relevant study staff will have access to the data collected as part of this research. Access to the study database will be restricted by role-based permission to authorised study personnel. will be suitably trained on the system prior to being granted access. Individual user accounts will be password-protected and will not be shared between members of the study team.

9.5 Archiving

Archiving of research data, source data, the ISF, consent forms and research-site related files will be arranged by Loughborough University according to local procedures. The TMF will be archived by the University of Leicester and stored for a minimum of 6 years after the study has ended. Storage will comply with the University of Leicester archiving Standard Operating Procedure. Details can be found at: https://le.ac.uk/research/regi/standard-operating-procedures. Destruction of essential documents will require authorisation from the Sponsor.

10 Quality Assurance Procedures

The study will be conducted in accordance with the current approved protocol, ICH GCP, the principals of the Declaration of Helsinki, relevant regulations and standard operating procedures (SOPs). The Principal Investigator (or their delegate) will be responsible for maintaining the Investigator Site File (as appropriate) and ensuring it is kept 'inspection ready' at all times. The Trial Master File (TMF) will be maintained by the University of Leicester and kept in a folder in a locked cabinet/drawer in a secured room in a secure office environment office at the University of Leicester by the Chief Investigator (or delegate).

10.1 Monitoring, audit and inspection

The University of Leicester as Sponsor operates a risk-based monitoring programme which this study will be subject to.

11 Protocol Compliance

11.1 Protocol deviations

A study related deviation is a departure from the ethically approved study protocol or other study document or process (e.g. consent process or administration of study intervention) or from Good Clinical Practice (GCP) or any applicable regulatory requirements. Planned deviations or waivers are not allowed however it is acknowledged that accidental protocol deviations may occur. Any deviations from the protocol will be documented in a protocol deviation form and filed in the Trial Master File/Investigator Site File as applicable.

If a protocol deviation occurs, then the CI (or delegate) will document this in accordance with the University's Standard Operational Procedure (SOP) Identifying and Reporting Deviations and Serious Breaches of GCP and/or the Protocol. Deviations from the protocol which are found to frequently recur will be explored and where necessary an amendment to the protocol will be made.

11.2 Serious breaches

A "serious breach" is a breach of the protocol or of the conditions or principles of Good Clinical Practice which is likely to affect to a significant degree –

- (a) the safety or physical or mental integrity of the study subjects; or
- (b) the scientific value of the research.

In the event that a serious breach is suspected the Sponsor will be contacted within one working day. In collaboration with the CI, the serious breach will be reviewed by the Sponsor and, if appropriate, the Sponsor will report it to the approving REC committee and the relevant NHS host organisation within seven calendar days.

12 Ethical and Regulatory Considerations

12.1 Research ethics committee (REC) and regulatory review, approvals/permission/support, compliance and reports

Once the Sponsor Review process is complete authorisation from the University of Leicester's Research Governance Office will be issued to book further regulatory review of the proposed research. NHS Research Ethics Committee and the Health Research Authority will then review the proposal. Agreement in principle is subject to the research receiving all relevant regulatory permissions. Submission for regulatory approvals will occur via the Integrated Research Application System (IRAS). The Chief Investigator will ensure that all regulatory approvals, the local approval at Loughborough University and sponsor green light are in place before participants are approached.

For any required amendment(s) to the study, amendment will be submitted to the sponsor in the first instance for review and approval to submit the amendment for external regulatory approval. Amendments must be implemented following all required ethical, competent authority, site and Sponsor approvals and in line with Sponsor Standard Operating Procedures.

The Research Governance Office's Standard Operating Procedures will be followed for the duration of the study.

The Chief Investigator will notify the REC when the study has ended by completing the end of study notification form and will submit a final report of the results within one year after notifying REC.

A study master file will be maintained for the duration of the study and will be stored for a minimum of 6 years after the study has ended.

12.2 Peer review

Prior to review by the sponsor, the protocol has been through the external peer review as part of the grant submission process. It was externally reviewed by seven experts.

12.3 Patient and public involvement

This pilot study is a direct consequence of the Public and Patient Involvement and Engagement group's involvement in the design of a funded study on the effectiveness of neuromuscular electrical stimulation as a treatment of sarcopenia in haemodialysis patients. Specifically, the group had concerns about the discomfort associated with NMES, which this pilot is attempting to address. The PPIE group meets bimonthly and will be updated on the progress of the study. Patients will also be involved in the study as participants.

12.4 Assessment and management of risk

No aspect of usual care will be altered during the involvement of HD patients in this study. The risk of adverse events requiring emergency care is estimated to be very low following a rigorous screening process employed in the present study. All instrumentation used in the study will be CE-marked. Participants will be explained that partaking in any tests is voluntary and that they can refuse specific tests without explaining why.

Research will take place at Loughborough University. To assess muscle function, participants will perform muscle contractions in a specifically designed isometric knee extension dynamometer (testing chair) instrumented with a strain gauge to measure muscle forces during knee extension contractions. Participants will be habituated to the performance of muscle contractions in the study, and a thorough warm-up involving a series of submaximal contractions will be performed initially. Discomfort and any risk of muscle strain will be minimised by performing static (rather than dynamic) contractions with the participants' legs restrained by a strap connected to a strain gauge. Participants will be informed that some delayed onset muscle soreness may occur due to repeated muscle contractions (as it is common with novel exercise), but this is expected to dissipate in the few days following testing.

Neuromuscular electrical stimulation (NMES) will be delivered using a commercially available device from a high-street provider. As per the systematic review of the National Institute for Health and Care Excellence (NICE) the technique has been deemed safe to use in chronic disease populations (NICE, IP1741). The warm-up associated with muscle function testing (see above) will be performed before NMES to minimise the very low risk of injury and/or delayed onset muscle soreness. There is a very rare, but potential effect of NMES interfering with implantable devices, and therefore participants with a pacemaker or a similar device will be excluded from the study.

Overall, this study is categorised as having no higher risk than that of standard medical care.

